Study Protocol with SAP

Title:

Evaluating the Safety and Efficacy of Fractionated Carbon Dioxide Therapy in Postoperative Lower Extremity Wound Healing

NCT number:

NCT03644849

Document date:

April 7, 2021

Upload date:

November 7, 2021

Purpose: This study will evaluate the efficacy and safety of laser therapy on postoperative lower extremity wound healing over 12 weeks. We will include adult patients who have undergone Mohs Micrographic Surgery on their lower extremities. Patients with poor immune systems, current pregnancies, uncontrolled diabetes, lower extremity venous or arterial disease will not be included in this study. After surgery patients will be randomized into two groups. One group will receive a single laser treatment immediately after their surgery on their wound while the other will not. The group not receiving laser therapy will undergo a sham laser therapy treatment. Immediately after therapy and 4, 8, and 12 weeks postoperative patients will have a follow up visit. During these visits patients wound size will be recorded, whether the wound has healed, a photograph will be taken, and the wound temperature will be measured. Patient will be given a diary to record any adverse events related to the wound and will fill out a quality of life survey.

Objectives (specific aims and hypotheses): We hypothesize that the AFL carbon dioxide ablative laser is a safe and efficacious treatment for lower extremity wounds that result from skin cancer surgery. We plan to test this hypothesis in 2 specific aims:

Aim 1. We will establish the safety and tolerability of the carbon dioxide AFL for postoperative lower extremity wounds. Patients with postoperative lower extremity wounds will be randomized to sham laser versus laser therapy. At designated time points 0-12 weeks after sham or laser treatment, patients will return to clinic for assessment of safety endpoints, including the incidence of wound infection and tolerability using a patient diary and health-related quality of life measured using a standardized generic questionnaire such as EQ. A sample size of 48 is appropriate.

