Blinding: There will be one unblinded member of the team in this study which will be the clinician performing laser therapy or sham therapy, who will therefore not be involved in any data collection, but will be responsible for reporting any adverse events per IRB protocols at our institution. Other members of the research team member will be blinded to patient group assignment, and these members of the research team will collect data (see below) at subsequent visit. Additionally, patients will be blinded to treatment group. This will be achieved by having patients wear safety glasses which blind them and the wound site still anesthetized from the operation. Data collection will be done by a separate research team member who is blinded to the treatment groups.

Inclusion Criteria: Eligibility criteria will include patients older than 18 years, those with a lower extremity wound as a result of Mohs Micrographic Surgery at Saint Louis University Dermatology Des Peres, and a postoperative wound greater than 5mm in diameter. Patients must be able to understand the informed consent, willing to come to the office for treatments and capable of following post-treatment instructions.

Exclusion Criteria: Exclusion criteria will include pregnancy, breast feeding, immunosuppression, uncontrolled diabetes (defined as $>7\%$ A1c in the last 3 months), peripheral vascular disease, venous insufficiency, decompensated heart failure (NYHA class IV), peripheral neuropathy involving the treatment site, active cancer at the time of study enrollment excluding curatively treated skin cancer, and any underlying or current medical condition which, in the opinion of the Investigator, would interfere with the evaluation of the subject, or no desire/unable to undergo laser therapy. Immunosuppression will be defined as patients with HIV, AIDS, who have received an organ transplant, allogeneic bone marrow transplant, or peripheral stem cell transplant, and any other patients taking chronic doses of systemic immunosuppressive medication within 6 months prior to randomization. Examples of immunosuppressive medications include Tacrolimus, Azathioprine, Prednisone, or Methotrexate.

Patient Visits and Data Collection:

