Patients will be seen at 4 separate visits to monitor safety and efficacy endpoints (4, 8 and 12 weeks post-operatively). The patient's initial visit will include preoperative screening for eligibility, informed consent procedure, and recording of past medical history and physical exam. Once the patient is deemed eligible, enrolled, and signed informed consent, they will be randomized to either carbon dioxide AFL therapy or sham laser therapy. After the patient undergoes Mohs surgery with the resultant ulcer (the defect that typically forms after Mohs), the patient will undergo either carbon dioxide laser versus sham laser therapy. We will determine presence or absence of complete healing, wound temperature, a digital photograph, quality of life, and adverse events at each visit. Healing will be determined by one of the licensed research team members and will be defined by complete epithelialization in the absence of scab/eschar.

Wound temperature will be recorded by noninvasive infrared thermographic camera. A digital photograph will be taken with a camera that has an attachment ensuring the same distance and angle at every visit. Quality of life will be determined by ED-5Q questionnaire. Adverse events will be recorded by eliciting an oral history and review of the patient's diary. Adverse events will be recorded as presence of absence of specific outcomes. Outcomes that patients will be directly questioned about include: crusting (scaly or thickened scar), swelling, burning sensation, xerosis at treatment site, pruritus at treatment site, infection, bleeding, hypertrophic or keloid scarring, burns, or color changes at treatment site. These data points will be collected at every visit, and adjudicated by a member of the research team blinded to the treatment group. Placebo treatment will consist of directing the laser system at the floor instead of the patient's wound site. The patients will be wearing safety glasses and will have their wound site still anesthetized from the operation therefore unaware if they are receiving the therapy. This group will serve as the control group to the treatment arm in the study.

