Statistical / Data analysis: We estimate that 48 participants will be required to show a significant difference in time to 100% epithelialization between treatment and control during the 12 week study. A power analysis conducted in R(1) using the powerSurvEpi package(2) with alpha = 0.10 and beta = 0.20 suggested 24 participants per group or 48 total were required. We will employ various statistical techniques in addressing our study aims. For our first aim, efficacy: time to epithelialization will be modeled in a Cox regression as a function of covariates and treatment status. Temperature will be similarly modeled, but for these outcomes we will examine effects across time via a linear mixed model. For our second aim, safety: we intend to model incidence of infection as well as quality of life again across time using linear mixed models but this time based on non-inferiority comparisons. To address any attrition, we will employ per-protocol analysis. In the interest of safety, we plan to perform interim analyses at one month and discontinue the study if warranted.

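### Does the one-month safety interim need a stated time origin, patient count and reviewer before it can be carried out?

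*Combined protocol and SAP*

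**What the plan says.** The interim has one sentence, in the Statistical / Data analysis section: "In the interest of safety, we plan to perform interim analyses at one month and discontinue the study if warranted". No other section adds a time origin, a number of patients, a criterion or a reviewer.

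The surrounding arrangements are these:

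- **Treatment.** The Purpose section states: "One group will receive a single laser treatment immediately after their surgery".
- **Visits.** The same section states: "Immediately after therapy and 4, 8, and 12 weeks postoperative patients will have a follow up visit". The first return visit is therefore at week 4.
- **Safety outcomes.** The Objectives section says "patients will return to clinic for assessment of safety endpoints, including the incidence of wound infection and tolerability using a patient diary". Patient Visits and Data Collection gives the list that patients are asked about at each visit, beginning "Outcomes that patients will be directly questioned about include: crusting (scaly or thickened scar), swelling, burning sensation" and going on to include infection and bleeding.
- **Who knows the arm.** The Blinding section says "There will be one unblinded member of the team in this study which will be the clinician performing laser therapy or sham therapy". That clinician collects no data but is "responsible for reporting any adverse events per IRB protocols at our institution". Everyone else on the team is blinded.
- **Adjudication.** Patient Visits and Data Collection says: "These data points will be collected at every visit, and adjudicated by a member of the research team blinded to the treatment group".

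**The concern.** Safety is one of the trial's two aims, and this sentence is all the plan says about interim review. Because the laser is applied once, straight after surgery, stopping early can spare only patients who have not yet been treated. How much protection the interim gives depends on when it happens, and one month can be read in three ways:

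- **Week-4 data as they accumulate.** The look can be done, but nothing says how many patients trigger it.
- **One calendar month after the study opens.** Hardly anyone would have reached the first return visit.
- **When every patient has reached one month.** All 48 would already have been treated.

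There is a second worry. If the arms are to be compared, the only person who knows the allocation is the treating clinician, who has no role in data collection. Nobody is then assigned to tabulate by arm, and doing so within the team could unblind the people who assess outcomes.

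**Working it through.** The plan gives no figure for the interim, so there is nothing to reproduce. The check asks how far the readings differ and what a more detailed rule would gain.

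**Inputs from the documents.** 48 patients, 24 per arm (Statistical / Data analysis); first return visit at week 4, taken as day 28 (Purpose); a study window of September 2018 to November 2020 that includes analysis and submission (Study Design).

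**Assumptions.** Even accrual over M = 24, 12, 9 or 6 months. The upper value is roughly the window less 12 weeks of follow-up. A month is 30.44 days. Infection rates are illustrative, since the documents give none.

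**1. One calendar month after opening.** Enrolled = 48/M. Expected number past week 4 = (48/M) × (30.44 − 28)/30.44. A 31-day month replaces 2.44 by 3 in the numerator.

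| M (months) | Enrolled at one month | Past week 4 (30.44 days) | Past week 4 (31 days) |
|---|---|---|---|
| 24 | 2.0 | 0.16 | 0.20 |
| 12 | 4.0 | 0.32 | 0.39 |
| 9 | 5.3 | 0.43 | 0.53 |
| 6 | 8.0 | 0.64 | 0.79 |

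The expected number reaches one only if all 48 accrue within 48 × 2.44 = 117 days, or 48 × 3 = 144 days for a 31-day month. On this reading the look holds almost no week-4 data.

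**2. When all have reached one month.** 48 of 48 are already treated, by definition.

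**3. Accumulating week-4 data.** When k patients have completed week 4, the number untreated is 48 − k − (48/M) × 28/30.44.

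- k = 12: 34.2, 32.3, 31.1 and 28.6 for M = 24, 12, 9 and 6.
- k = 24: 22.2, 20.3, 19.1 and 16.6.

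So a review early or midway leaves a substantial share of patients to protect.

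**4. Which reading do the documents support?** The Purpose section puts the first return visit at week 4, when the listed safety outcomes are collected. That matches one month. Nothing in the text ties the month to the opening date. The last reading fits poorly with an intention to discontinue the study, because no treatment would remain to be withheld. The word analyses is also plural, which allows repeated review as patients reach week 4.

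**5. What would a fixed-count, by-arm look show?** As an illustration only, and not as a stopping rule, take the chance that laser shows at least two more infections than sham. With independent binomial counts X (laser) and Y (sham) and an equal split, this is P(X − Y ≥ 2).

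| Rates, laser v sham | 6 v 6 | 12 v 12 |
|---|---|---|
| 10% v 5% | 8.8% | 22.5% |
| 20% v 5% | 27.7% | 56.4% |
| 30% v 5% | 48.8% | 80.5% |
| 5% v 5% (chance) | 2.5% | 7.1% |
| 10% v 10% (chance) | 6.6% | 14.4% |
| 20% v 20% (chance) | 13.4% | 21.9% |

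Only large differences stand out. With 6 per arm, a doubling from 5% to 10% is flagged about as often (9%) as chance alone flags two arms that both run at 10% (7%).

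**The case for a change.** The strongest case for a change is that the sentence cannot be carried out without choosing among readings that protect very different numbers of patients: on an early or mid-trial week-4 look about 17 to 34 are still untreated, and on the last reading none. Even the week-4 reading supplies only a per-patient origin; the look could rest on 1 patient or on 48. Reporting of single adverse events to the IRB is not a review of accumulating rates. Stating a trigger would take a sentence, with no extra patients or visits.

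Some of this stands. The origin, the count, the pooled or by-arm status and the reviewer are all unstated, and the adverse event reporting duty does not replace an interim review.

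The rest carries less weight. The damaging consequences come only from the two readings that the text does not support. Freedom to choose when to look is a serious fault when efficacy is tested or when the person choosing sees the arms. Here the stated purpose is safety, and everyone but the treating clinician is blinded. The reviewer gap exists only if a comparison by arm is meant. A pooled review by the blinded team fits the Blinding section as it stands, though it cannot show a difference between arms. A by-arm review would need one more unblinded person, for the limited sensitivity shown above.

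**Conclusion.** The omission is real but small, and it does not call for a change. The plan states no rule that gives a wrong result. It leaves a definition unwritten, and the visit schedule points to a sensible way to fill it: review the safety data as patients reach week 4. On that reading the interim is workable and comes while patients remain to be protected, provided it is held early or midway.

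The alarming figures (fewer than one patient expected past week 4, or all 48 already treated) belong to readings that no section supports. The first of them also depends on even accrual over 6 months or more. The gain from a fixed-count, by-arm schedule is modest under the assumed infection rates: 22.5% against 14.4% with 12 per arm, and 8.8% against 6.6% with 6 per arm, for 10% v 5% set against equal rates of 10%. Set against the lower chance level at equal rates of 5% the contrast is wider (7.1% and 2.5%), but detection stays low.

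A design change may also come too late: the document is dated April 2021 and the Study Design section planned completion by November 2020. If enrolment is over, what remains is ordinary reporting: when the interim took place, on how many patients, who saw the data, and whether efficacy was examined.
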